8.2.1.3 Medical History

All medical history shall be classified as either past or present disease based on the first BESPONSA® administration date and shall be summarized using frequency and percentage by System Organ Class(SOC) and Preferred Term (PT) of MedDRA version 22.1(or the latest version at the time of analysis).

- Past disease: Yes | No
- Present disease: Yes | No
- Veno-occlusive liver disease/Sinusoidal obstruction syndrome(VOD/SOS): Yes | No
- Hepatic disorder : Yes | No
- Severity of hepatic disorder: Mild | Moderate | Severe | Unknown
- Renal disorder: Yes | No
- Severity of renal disorder: Mild | Moderate | Severe | Unknown
- Allergic history: Yes | No

8.2.1.4 Concomitant Medication

All concomitant medication including the transfusion while BESPONSA® is being administrated shall be summarized using frequency and percentage by ATC code level 1 and level 3.

- Concomitant medication: Yes | No

PFIZER CONFIDENTIAL

8.2.1.5 Administration status of BESPONSA®

- BESPONSA® total administration period(day):
Last administration date of last cycle – First administration date of first cycle + 1
- Total administration cycle:
Cycle 1 | Cycle2 | Cycle3 | Cycle 4 | Cycle 5 | Cycle 6
- Total administration dose(mg)
- Administration dose(mg) per cycle

8.2.2 Safety Analyses

The safety analyses will be performed for Safety analysis set. And all adverse events (AE) will be standardized by MedDRA version 22.1 (or the latest version at the time of analysis).

Adverse events which causality is missing or not 'unlikely' will be considered as adverse drug reaction (ADR).

8.2.2.1 Adverse event

The following adverse events shall be summarized by SOC and PT using the number of subjects(n), percentage (%), number of events, and 95% confidence interval of percentage.

- AE·ADR
- Serious AE·ADR
- Unexpected AE·ADR
- Unexpected serious AE·ADR

The following characteristics of adverse events shall be summarized by SOC and PT using the number of event and percentage(%).

If missing is found, the number of event and percentage(%) of missing will be presented at the bottom of each characteristics.

- Severity: G1 | G2 | G3 | G4 | G5
- Action:
Withdrawn (temporarily or permanently, or delayed) | Dose reduced | Dose increased | Dose not changed | Unknown | Not applicable
- SAE Category:
Results in death | Is life-threatening | Requires inpatient hospitalization or prolongation of hospitalization | Results in persistent or significant disability/incapacity (substantial disruption of the ability to conduct normal life functions) |

- Results in congenital anomaly/birth defect |
Is important medical event (if it is determined that the event may jeopardize the subject or may require intervention to prevent one of the other outcomes listed in the definition above)
- Outcome:
Recovered | Recovered with sequelae |
Recovering | Not recovered | Unknown
- Causality of AE to the study drug:
Certain | Probable/likely | Possible | Unlikely |
Conditional/unclassified | Unassessable/unclassifiable
- Other causality of AE:
Disease under the study | Other disease |
Concomitant treatment drug or non-drug | Others

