7.2.3. Duration of the study

According to MFDS re-examination regulation, the re-examination report based on collected data of 6 years must be submitted to MFDS within 3 months after the end of specified re-examination period (from the product approval date to 6 years afterwards).

The data collection period of this study is until the required subject number (100 patients) is collected. The observation period for each subject is from initiating administration of first dose of BESPONSA® to the end of the observation period of the study, which must include at least 28 calendar days following the last administration of a BESPONSA®. In case of patient that Hematopoietic Stem Cell Transplant (HSCT) after administrated BESPONSA®, follow-up until 180 days after transplantation. All the data collected during the observation period should be recorded in the case report form (CRF). In case of an adverse event/safety event recognized after the observation period ends, it should be recorded in the CRF as specified in Section 7.

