7.3.8.3. Adverse events data collection

The investigator collects data on safety events as specified in Section 7 including all adverse events that occur during the observation period regardless of causal relationship to BESPONSA®. The information on adverse events should include the specific conditions or events, duration of the events (start date and stop date), severity, actions taken, seriousness (serious or non-serious), outcome and causal relationship to BESPONSA®.

Check either 'yes' or 'no' in adverse event occurrence section. If 'yes', record in detail.

- Adverse events: Record the name of adverse event. If possible, specify diagnosis, not individual symptoms. Record the name according to '*National Cancer Institute (NCI) Common Terminology Criteria for Adverse Events (CTCAE) Version 4.0*¹⁰'.

- Date of onset: Record the date of onset. Record approximate date if an actual date is unknown.
- Severity: Severity evaluation of AE must be done according to grades of 'NCI CTCAE Version 4.0¹⁰'. If the severity of an AE changed, the AE must be entered separately. Record stop date of previous severity and onset date of new severity – along with completion of all other items.
- Action: Check relevant action of BESPONSA® dosage. Select one among 'withdrawn (temporarily or permanently, or delayed)', 'dose reduced', 'dose increased', 'does not changed', 'unknown', or 'not applicable'.
- Seriousness: Check either 'yes' or 'no'. If 'yes', record the appropriate number for the category of seriousness.

A serious adverse event is any untoward medical occurrence at any dose that:

- ① Results in death;
- ② Is life-threatening;
- ③ Requires inpatient hospitalization or prolongation of hospitalization;
- ④ Results in persistent or significant disability/incapacity (substantial disruption of the ability to conduct normal life functions);
- ⑤ Results in congenital anomaly/birth defect.
- ⑥ Is important medical event (if it is determined that the event may jeopardize the subject or may require intervention to prevent one of the other outcomes listed in the definition above)

Check the following at the end of the study or after the resolution of AE.

- Outcome: Check one among 'Recovered', 'Recovered with sequelae', 'Recovering', 'Not recovered' or 'Unknown' as a reply to a question; 'Is the AE still present?'. If the status has resolved, record the date of resolution. Record approximate date if an actual date is unknown.

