9.2. Reporting period

For each patient, the safety event reporting period begins at the time of the patient's first dose of BESPONSA®, or the time of the patient's data privacy statement if s/he is already exposed to BESPONSA®, and lasts through the end of the observation period of the study, which must include at least 28 calendar days following the last administration of a drug under study; a report must be submitted to Pfizer Safety (or its designated representative) for any of the types of safety events listed in the table above occurring during this period. If a patient was administered a drug under study on the last day of the observation period, then the reporting period should be extended for 28 calendar days following the end of observation.

Most often, the date of data privacy statement is the same as the date of enrollment. In some situations, there may be a lag between the dates of data privacy statement and enrollment. In these instances, if a patient provides data privacy statement but is never enrolled in the study (e.g., patient changes his/her mind about participation), the reporting period ends on the date of the decision to not enroll the patient.

If the investigator becomes aware of a SAE occurring at any time after completion of the study and s/he considers the SAE to be related to BESPONSA®, the SAE also must be reported to Pfizer Safety.

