2.1 STUDY DESIGN

This is a prospective, observational, non-interventional, multi-center study in which subjects will be administered as part of routine practice at Korean health care centers by accredited physicians. The study can be performed in Korean health care centers where BESPONSA® is prescribed to treat the relapsed or refractory B-cell precursor ALL.

All subjects enrolled should meet the usual prescribing criteria for BESPONSA® as per the local product document (LPD) and should be entered into the study at the physician's discretion.

Duration of the Study

According to MFDS re-examination regulation, the re-examination report based on collected data of 6 years must be submitted to MFDS within 3 months after the end of specified re-examination period (from the product approval date to 6 years afterwards).

The data collection period of this study is until the required subject number (100 patients) is collected. The observation period for each subject is from initiating administration of first dose of BESPONSA® to the end of the observation period of the study, which must include at least 28 calendar days following the last administration of a BESPONSA®. In case of patient that Hematopoietic Stem Cell Transplant (HSCT) after administrated BESPONSA®, follow-up until 180 days after transplantation. All the data collected during the observation period should be recorded in the case report form (CRF). In case of an adverse event/safety event recognized after the observation period ends, it should be recorded in the CRF.

Sample Size

CCI

CCI

period. CCI

100 subjects will be collected during re-examination

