8.2.2.2 Factor analysis for adverse events

To identify factors that may be associated with AEs, AEs according to the background factors in section 8.2.1 and special population set in section 5.3 shall be summarized using the number of subjects(n), percentage(%), number of events and the 95% confidence interval of percentage. In addition, to explore the factors that affect the occurrence of AE, univariate analyses based on a Chi-square test or Fisher's exact test(when cells with an expected frequency of less than 5 exceed 20% of total cells) and logistic regression shall be used to assess the impact of each background factor on the AE occurrence and p-value will be provided.

For the final re-examination report, potentially significant factors(p-value<0.05) identified in the univariate analyses will be further explored in a multiple logistic regression model. For final models, odds ratio, 95% confidence interval of odds ratio and p-value will be provided for each factor. If there is no potential significant factor identified in the univariate analyses, multivariate analysis with logistic regression will not be applied.

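### Adverse event percentages and factor tests ignore unequal follow-up (at least 28 days after last dose, but 180 days after HSCT), so they partly reflect how long patients were watched

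*SAP*

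**What the plan says.** **Follow-up.** Protocol 7.2.3 and SAP 2.1 observe each patient from first dose to the end of the observation period, "which must include at least 28 calendar days following the last administration of a BESPONSA". Transplanted patients have a longer rule: "In case of patient that Hematopoietic Stem Cell Transplant (HSCT) after administrated BESPONSA®, follow-up until 180 days after transplantation". Protocol 9.2 defines the safety reporting period as one that "lasts through the end of the observation period of the study, which must include at least 28 calendar days" after the last dose, and does not repeat the HSCT extension.

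**AE collection.** Protocol 7.3.8.3 collects "all adverse events that occur during the observation period regardless of causal relationship to BESPONSA". Protocol 7.2.3 adds: "In case of an adverse event/safety event recognized after the observation period ends, it should be recorded in the CRF".

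**AE analysis.** SAP 8.2.2.1 gives subjects, percentage, "number of events, and 95% confidence interval of percentage" by SOC and PT, and SAP 8.2.2.3 does the same for the elderly, hepatic and renal subsets. The default interval is Clopper-Pearson (SAP 8.1.3). SAP 8.2.2.2 tabulates "AEs according to the background factors in section 8.2.1", tests AE occurrence by chi-square or Fisher and by logistic regression, and for the final report carries factors with p<0.05 into a multiple logistic model that reports odds ratios.

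**What is absent.** SAP 8.2.2 has no onset window, person-time rate, offset, censoring rule or split before and after HSCT. The transplant factor in SAP 8.2.1.2 is previous transplant only. Censoring is defined for PFS, OS and DoR, but not for safety.

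**The concern.** A crude percentage with an exact binomial interval treats each patient as one equal opportunity to have an event. Here a transplanted patient can be observed for about six months longer than the protocol requires for a patient who is not transplanted, and everything in that time is collected whatever its cause.

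Two things follow. The pooled percentage depends on how many patients go on to HSCT. And a background factor that is related to HSCT (age or disease status could plausibly be) can appear associated with AEs although the event rate per day is the same at all its levels. No listed covariate corrects this. Total administration period and number of cycles (SAP 8.2.1.5) describe treatment length, not the post-transplant extension.

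The ADR rule extends the problem to drug reactions. Under SAP 7 and 8.2.2, an AE whose causality is missing or anything other than unlikely counts as an ADR. A post-transplant event judged unclassifiable is therefore a drug reaction in the tables. These percentages and odds ratios go into the re-examination report.

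**Working it through.** The plan states no figure to reproduce: it gives no AE rate, HSCT share or distribution of follow-up. The checks below show the mechanism under stated assumptions.

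**1. AEs starting after the last dose.**
From the documents: 28 days and 180 days. Assumed: a constant AE risk r per 28 days, the same for everyone; follow-up of exactly 28 days without HSCT and 180 days after the last dose with HSCT; no deaths. (The 180 days actually start at transplant, which comes later.)

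Probability of an AE within 180 days = 1 − (1 − r)^(180/28).
- r = 5%: 5% in 28 days, 28% in 180 days
- r = 10%: 10% and 49.2%
- r = 15%: 15% and 65%

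Take a factor with no effect on risk, HSCT in 60% of one level and 5% of the other, and r = 10%:
- level A: 0.60 × 0.492 + 0.40 × 0.10 = 0.335
- level B: 0.05 × 0.492 + 0.95 × 0.10 = 0.120
- odds ratio = (0.335/0.665) / (0.120/0.880) = 3.7

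With HSCT in 40% versus 10%, the risks are 0.257 and 0.139, and the odds ratio is 2.1.

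**2. Any AE, which is the outcome in SAP 8.2.2.2.**
AEs count from the first dose. Add an on-treatment AE risk q, assumed equal in both levels and independent of later events: P = 1 − (1 − q)(1 − p), where p is the level's risk from step 1 (r = 10%).

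| q | HSCT 60% vs 5%: risks | Odds ratio | HSCT 40% vs 10%: odds ratio |
|---|---|---|---|
| 0 | 33.5% vs 12.0% | 3.7 | 2.1 |
| 20% | 46.8% vs 29.6% | 2.1 | 1.5 |
| 50% | 66.8% vs 56.0% | 1.6 | 1.3 |
| 80% | 86.7% vs 82.4% | 1.4 | 1.2 |

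The spurious odds ratio shrinks as on-treatment AEs become common, but stays above 1.

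**3. How often the SAP's test would flag such a factor.**
Simulation: 100 patients, 6,000 runs, the SAP's chi-square/Fisher rule, one constant hazard for everyone. Assumed: 60 days of treatment and 30 days from last dose to HSCT, so follow-up is 60 + 28 = 88 days without HSCT and 60 + 30 + 180 = 270 days with it. An AE with 20% risk without HSCT then has 49.6% risk with it. The factor has no effect on the hazard. Share of runs with p<0.05:

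| AE risk without HSCT | Factor 50/50, HSCT 60% vs 20% | Factor 25/75, HSCT 10% vs 50% | Factor 50/50, no link to HSCT |
|---|---|---|---|
| 10% | 16% | 8% | 5.2% |
| 20% | 24% | 19% | 5.1% |
| 40% | 37% | 30% | 5.7% |
| 80% | 22% | 14% | 4.5% |

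**4. The pooled percentage.**
In the same setting, the 20% AE shows a pooled percentage of 25.9% if 20% of patients have HSCT (0.2 × 49.6 + 0.8 × 20) and 37.7% if 60% do (0.6 × 49.6 + 0.4 × 20), at an identical daily rate.

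**5. Does a window ending 28 days after the last dose equalise time at risk?**
It removes the HSCT extension, but not differences in treatment length. With assumed treatment of 21 to 120 days, the window runs from 49 to 148 days. At 10% per 28 days it captures 1 − 0.9^(49/28) = 17% to 1 − 0.9^(148/28) = 43%.

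**The case against.** The strongest counter-arguments, and what stands of each:

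- **The largest odds ratio is not for the SAP's outcome.** This stands. A reader might take 3.7 as the bias in the any-AE factor test. It applies only to AEs starting after the last dose. Protocol 7.3.8.1 counts disease worsening, lack of efficacy and qualifying laboratory findings as AEs, so on-treatment risk is unlikely to be near zero.
- **28 days is a minimum.** This stands. Actual follow-up without HSCT is not stated and may be longer, and death shortens follow-up. Both affect size, not the mechanism.
- **Not every HSCT-linked factor will appear linked to AEs.** This stands. With a 40-point imbalance in HSCT, 8% to 37% of simulated runs reach p<0.05, so most do not. Unrelated factors stay near 5%.
- **Pooling of late-recognised AEs is inferred.** This stands. A reader might conclude that the SAP pools them by rule. It does not say how they are tabulated, and an event recognised late need not have started late. This is a gap to close.
- **The study is descriptive.** SAP 4 draws no definite conclusions from p-values, and Protocol 7.9 acknowledges the limits of an uncontrolled design. This lowers the consequence, but the percentages and odds ratios are still reported.
- **A restricted window could push post-transplant reactions out of the main tables.** This would matter if the window replaced the all-AE tables, since serious and unexpected reactions are study objectives. It does not apply if the restricted tables are added.

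**Conclusion.** The point holds in a limited form. Follow-up differs by HSCT by design, and SAP 8.2.2 neither fixes a window nor accounts for time at risk. AE percentages, and associations for factors related to HSCT, therefore partly reflect follow-up length. The documents do not support the wider inference that all factor associations are artefacts.

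The size cannot be fixed from the documents. With an assumed 10% AE risk per 28 days and HSCT in 60% versus 5%, the spurious odds ratio for any AE is about 2.1, 1.6 and 1.4 at on-treatment risks of 20%, 50% and 80%; with HSCT in 40% versus 10% it is 1.5, 1.3 and 1.2. All of this rests on a constant, equal hazard, follow-up at the 28-day minimum without HSCT, and no deaths. If almost every patient has some AE, the any-AE test is affected least, while less common events by SOC and PT remain exposed.

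This should be corrected. Because the analyses are exploratory, it is not critical.

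**What to change.** In SAP 8.2.2:

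1. Keep the all-AE tables.
2. Add parallel AE and ADR tables restricted to onset from first dose to 28 days after last dose. This is the post-dose period the protocol requires for every patient, and it needs only administration dates (Protocol 7.3.6) and AE onset dates (Protocol 7.3.8.3), both already collected. Some onset dates may be approximate, so state how those are assigned.
3. Base the factor analysis (Tables 25–27) on that window, with an offset for time at risk or a time-to-event method, because the window still varies with treatment length and death.
4. Tabulate later-onset AEs, including post-HSCT and late-recognised events, separately by time since last dose, and state how late-recognised AEs are assigned. Split by HSCT only where the HSCT date is available: the CRF items listed in the protocol give a date for previous HCT and a tick for planned or ongoing HCT, but no date for HSCT after BESPONSA.

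The cost is SAP wording and a few extra tables. The AE percentage in the restricted window will be somewhat lower than the all-AE figure, so the two should be shown side by side. Patient follow-up and data collection do not change.

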7.7.1. Safety analysis

- Safety parameter
 - Count and frequency of occurrence of adverse event, serious adverse event, adverse drug reaction or unexpected adverse event by category.
 - Count and frequency of occurrence of adverse events by subject baseline factor and by treatment factor to determine factors affecting the safety.
- Sub-analysis may be performed utilizing factors which are considered to affect safety. If required, chi-square test (χ^2 -test) will be used for subgroup analysis.

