8.2.2.3 Adverse event in special population set

Adverse events reported from special population set in section 5.3 shall be summarized by SOC and PT using the number of subjects(n), percentage(%), number of events and 95% confidence interval of percentage.

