8.2.4 Non-safety population Analyses

The following adverse events from non-safety population shall be summarized by SOC and PT using the number of subjects(n), percentage(%), number of events and 95% confidence interval of percentage.

- AE·ADR
- Serious AE·ADR
- Unexpected AE·ADR
- Unexpected serious AE·ADR

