9. LIST OF TABLES AND TABLE SHELLS

Section I. Analysis for MFDS

Table 1. Patient disposition

Table 2. Demographics and underlying disease information

Table 3. Previous systemic therapy

Table 4. Previous hematopoietic cell transplant

Table 5. Past disease

Table 6. Present disease

Table 7. Veno-occlusive liver disease/Sinusoidal obstruction syndrome(VOD/SOS)

Table 8. Hepatic disorder

Table 9. Renal disorder

Table 10. Allergic history

Table 11. Concomitant medication

Table 12. Administration status of BESPONSA® – Total

Table 13. Summary of Adverse Events

Table 14. Adverse event – AE·ADR

Table 15. Adverse event – Serious AE·ADR

Table 16. Adverse event – Unexpected AE·ADR

Table 17. Adverse event – Unexpected serious AE·ADR

Table 18. Characteristics of adverse events

Table 19. Adverse events by Severity by SOC/PT

Table 20. Adverse events by Action taken by SOC/PT

Table 21. Adverse events by SAE categories by SOC/PT

Table 22. Adverse events by Outcome by SOC/PT

Table 23. Adverse events by Causality to the study drug by SOC/PT

Table 24. Adverse events by Other causality by SOC/PT

Table 25. Categorical factor analysis for adverse events

Table 26. Continuous factor analysis for adverse events

Table 27. Multiple logistic regression for adverse event for the final re-examination

Table 28. Adverse event in elderly(≥65 years) group

Table 29. Adverse event in hepatic disorder group

Table 30. Adverse event in renal disorder group

Table 31. Response evaluations

Table 32. Last effectiveness

Table 33. Categorical factor analysis for last effectiveness

Table 34. Continuous factor analysis for last effectiveness

Table 35. Multiple logistic regression for last effectiveness for the final re-examination

Table 36. Effectiveness(Best overall response)

Table 37. Categorical factor analysis for effectiveness(best overall response)

Table 38. Continuous factor analysis for effectiveness(best overall response)

Table 39. Multiple logistic regression for effectiveness(best overall response) for the final re-examination

Table 40. Non-safety population – AE·ADR

Table 41. Non-safety population – Serious AE·ADR

Table 42. Non-safety population – Unexpected AE·ADR

Table 43. Non-safety population – Unexpected serious AE·ADR

Table 44. Non-PMS Analyses – AE·ADR

Table 45. Non-PMS Analyses – Serious AE·ADR

Table 46. Non-PMS Analyses – Unexpected AE·ADR

Table 47. Non-PMS Analyses – Unexpected serious AE·ADR

Section II. Analysis for publication

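### AE severity and other characteristics are tabulated by event only, although each grade change opens a new AE entry: no rule joins entries or gives the worst grade per subject

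*SAP*

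**What the plan says.** **Data collection.** Protocol 7.3.8.3 instructs the site: "If the severity of an AE changed, the AE must be entered separately". The old grade gets a stop date and the new grade an onset date, "along with completion of all other items". Action, seriousness, outcome and causality are therefore recorded again for each entry.

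**Analysis.** SAP 8.2.2.1 has two parts.
- AEs and ADRs (all, serious, unexpected, unexpected serious) are summarised by number of subjects, percentage, number of events and a 95% CI.
- For the characteristics the unit is the event alone: "The following characteristics of adverse events shall be summarized by SOC and PT using the number of event and percentage". These are severity (G1 to G5), action, SAE category, outcome, causality and other causality.

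The table list in SAP section 9 matches this. Its severity table is "Table 19. Adverse events by Severity by SOC/PT", and no table of subjects by worst grade is listed.

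**Other tables with an event count.** The factor summaries (SAP 8.2.2.2) include a number of events. So do the special-population tables ("Adverse events reported from special population set in section 5.3 shall be summarized by SOC and PT") and the non-safety tables ("The following adverse events from non-safety population shall be summarized by SOC and PT").

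**What is absent.** The SAP does not say what counts as one event, how entries of the same AE are linked, or what the denominator of the characteristic percentages is. Its only rule on duplicates (SAP 5.1, item 6) concerns patients enrolled more than once.

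**The concern.** Protocol 7.7.1 names the safety parameter as "Count and frequency of occurrence of adverse event, serious adverse event, adverse drug reaction or unexpected adverse event by category". The entry rule makes the number of entries depend on how often the grade moved. The SAP then takes the number of events as its only unit for severity and the other characteristics. An AE recorded as G2-G3-G4-G2 is one episode in one subject but four entries.

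Two things are at stake. First, event totals and the percentages built on them give more weight to episodes whose grade changed often. Second, a safety reader will want to know how many patients had, say, a given PT at Grade 3 or higher, and the planned tables do not answer that.

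For effectiveness, by contrast, the SAP does reduce repeated evaluations to one value per patient: the last (8.2.3.2) and the best overall response (8.2.3.5). Repeated grades of one AE get no such rule.

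**Working it through.** The documents give no AE rates and no figure on this point, so there is nothing to reproduce. All counts below are assumptions chosen to show the mechanism. Percentages use entries of the same PT as denominator, which is also an assumption.

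**1. Same output, different truth.** Take 9 subjects with one episode each, entries at Grade 3 or 4 only, and neighbouring entries that differ in grade. The table prints 18 events: Grade 3 12/18 = 66.7%, Grade 4 6/18 = 33.3%.

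Let k be the number of subjects with any Grade 4 entry.
- Upper limit: there are 6 Grade 4 entries, so k ≤ 6.
- Lower limit: a subject with a Grade 4 entries needs at least a − 1 Grade 3 entries between them. The k subjects together need at least 6 − k. The other 9 − k subjects have one Grade 3 entry each. The Grade 3 total is therefore at least (6 − k) + (9 − k) = 15 − 2k. With 12 such entries, 15 − 2k ≤ 12, so k ≥ 1.5, that is k ≥ 2.

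Both limits can be reached:

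| Pattern | Grade 3 entries | Grade 4 entries | Subjects with worst Grade 4 |
|---|---|---|---|
| 3 × G3-G4-G3, 3 × G3-G4, 3 × G3 | 6 + 3 + 3 = 12 | 3 + 3 = 6 | 6/9 = 66.7% |
| 1 × G4-G3-G4-G3-G4, 1 × G3-G4-G3-G4-G3-G4, 7 × G3 | 2 + 3 + 7 = 12 | 3 + 3 = 6 | 2/9 = 22.2% |

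In both, 9 episodes appear as 18 events.

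**2. Grades that only worsen.** Four subjects go G2-G3-G4 and five stay at G3. Entries: 4 × 3 + 5 = 17. The Grade 4 count of 4 now equals the number of subjects, but the printed share is 4/17 = 23.5% against 4/9 = 44.4% of subjects.

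**3. Direction of the error.** Take 100 episodes, 40 of them peaking at Grade 3 or higher, so the share by episode is 40.0%.
- If each severe episode also has 1, 2 or 3 entries at Grade 1-2, the share by entry is 40/140 = 28.6%, 40/180 = 22.2% or 40/220 = 18.2%.
- If each severe episode runs G3-G4-G3, it is 120/180 = 66.7%.

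The printed share can be too low or too high.

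**4. Event totals.** If a share f of episodes changes grade and each of those has m entries, the total is multiplied by 1 + f(m − 1). With f = 0.1 and m = 2 this is 1.1. With f = 0.5 and m = 5 it is 3.0.

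**5. Outcome.** Suppose every entry carries the final outcome of its AE. In the first pattern of step 1, let 3 of the 9 episodes be not recovered (33.3%). If these are the three episodes with three entries, the table prints 9/18 = 50.0%. If they are those with two entries, it prints 6/18 = 33.3%, and if those with one entry, 3/18 = 16.7%. The share is weighted by the number of grade changes even when every site codes alike.

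**The case against.** **The main safety results stand.** This is correct. Number of subjects, percentage and 95% CI count a subject once per PT however many entries there are. The factor tests use the occurrence of any AE. No test or CI is planned on the event-level characteristics, and SAP section 4 states no hypothesis. A reader might infer that AE incidence is misreported; the documents do not support that.

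**Outcome coding.** A reader might also infer that the outcome table turns on whether sites code an entry closed by a grade change as recovered or not recovered. The text does not bear this out. Protocol 7.3.8.3 has outcome checked at the end of the study or after the AE resolves, as the reply to whether the AE is still present. It can fairly be read as giving every entry the final outcome of the AE. What remains is the weighting in step 5.

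**The SAP does not say to count rows.** The term event is undefined, and the table shells are visible only as titles, so a rule in an unseen shell cannot be excluded. But none is stated. If event were silently read as episode, a rule for choosing grade, action and causality would still be missing.

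**The examples are extreme.** The 2/9 case and the factor 3.0 need many grade changes in few subjects or episodes. They show what the tables cannot distinguish, not what will happen.

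**Event-level severity is a legitimate description.** It is, and it can stay. It does not replace the count of subjects by worst grade.

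**Conclusion.** The concern holds for AEs whose grade changes, not for every AE. For these, one episode is counted several times in Tables 18 to 24. In the SAE category table this happens only where more than one entry of the episode is flagged serious. The same repetition enters the event columns of the overall, factor, special-population and non-safety tables. How many subjects reached each worst grade cannot be read from the planned output.

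The real size is unknown, because it depends on how often grades change and the documents say nothing on that. The range of 22.2% to 66.7% rests on the assumed 9 subjects and 18 entries, with entries of the PT as denominator.

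This is more than missing detail: a tabulation of subjects by worst grade answers the safety question better and uses data already collected. It is a correction to descriptive event-based tables that should be made before the final analysis. It does not put the subject-level results in doubt.

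**What to change.** In SAP 8.2.2.1:

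1. **Define an event as one episode.** Join consecutive entries of the same PT in the same subject where one entry stopped and the next began because the grade changed. State a date tolerance, or require a query, for approximate dates.
2. **Set one value per episode.** Take the highest grade, the last outcome and the most severe action. Count the episode as serious if any entry is serious. Take the strongest causality, so that the episode is an ADR if any entry has causality missing or other than unlikely. This agrees with SAP 8.2.2. Write down the order of the action and causality categories in advance.
3. **Use joined episodes** for the characteristics in Tables 18 to 24 and for every number-of-events column drawn from the CRF.
4. **Extend Table 19** with number and percentage of subjects by worst grade, by SOC and PT, with the number of subjects in the safety analysis set as denominator. Keep event counts alongside, with episodes as denominator.

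**Cost.** A few sentences in the SAP, a small programming task to link entries, and a changed layout for Table 19. Dates, grades, action, seriousness, outcome and causality are already on the CRF, so no new data collection is needed. The drawback is that protocol 7.3.8.3 lists no field linking entries and allows approximate dates. Some links will be uncertain, and a tolerance that is too wide could merge separate episodes.
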